2 OBJECTIVES

Aim 1: Investigate the efficacy and safety of olanzapine in the treatment of nondiabetic gastroparesis.

We will utilize the gastroparesis cardinal symptom index daily diary (GCSI-DD) and an appetite visual analog scale (VAS) to compare severity of symptoms before and after treatment with olanzapine. Subjects will undergo regular testing of blood glucose, insulin, hemoglobin (Hgb) A1c, body mass index (BMI), liver enzymes, thyroid stimulating hormone (TSH), and prolactin levels during the study as well as after treatment completion to determine the safety of the medication. All adverse events will be compiled to investigate the tolerability of the medication.

Aim 2: Determine whether olanzapine has prokinetic effects on gastric emptying in gastroparesis.

We aim to test gastric motility, including gastric emptying and antroduodenal contractility parameters, by wireless motility capsule (WMC) before and at the completion of the study to determine if olanzapine has any pro-motility effects in gastroparesis.

Aim 3: Examine the effects of olanzapine on neurohumoral regulation of eating and appetite.

We seek to determine whether olanzapine promotes secretion of ghrelin in gastroparesis.

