6 STUDY DESIGN AND PROCEDURES

This is a pilot study of 10 consecutive subjects ages 18 – 80 with documented delayed gastric emptying within the past 2 years and history of nausea, vomiting, bloating, anorexia, early satiation, post-prandial fullness, and weight loss for at least 6 months without structural or organic cause will be enrolled. This will be an open label trial without a placebo arm to determine efficacy and safety of the medication in this population. This will be a single center study with subjects being enrolled at the University of Michigan. [name] at Massachusetts General Hospital will act as a co-I and will assist with data analysis but will not enroll any patients. [name] will receive only de-identified information.

The study will consist of a screening/baseline period of up to 30 days, an 8-week treatment period, and a 14-day post treatment safety follow-up visit and assessment of symptoms.

Screening/Baseline:

Subjects will participate in a screening/baseline visit within 30 days prior to study dosing. Subjects will be instructed to fast prior to the screening visit at which time they will undergo blood sampling for complete blood count (CBC), complete metabolic panel (CMP), lipid profile, insulin, Hgb A1c, prolactin, TSH, and urine or blood pregnancy screen (if applicable). A baseline ECG will also be performed. Ghrelin levels will be measured. Baseline vital signs, height, weight, and BMI will also be calculated. They will also have their gastric emptying assessed by wireless motility capsule (WMC). To be eligible for the study, the subjects' gastric emptying time, as determined by WMC, needs to be greater than 5 hours. Potential subjects will complete the gastroparesis cardinal symptom index daily diary (GCSI-DD) evaluation, appetite visual analog score (VAS), and Bristol Stool Form Scale (BSFS) for a minimum of 7 days to determine baseline level of symptoms [41]. Questionnaires will be completed in the evening after dinner. Mean total GCSI-DD score must be ≥ 2 in order to qualify for the study.

Week 1 – Week 8:

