Subjects will initially start on olanzapine 2.5 mg by mouth daily to be taken at bedtime. Subjects will return on days 7 and 14 to determine response to medication. Medication dose can be increased to 5 mg on day 7 and 10 mg on day 14, respectively, based on incomplete symptom response, which is defined as a mean change in GCSI-DD score < 0.5 from baseline. Height and weight will be measured on Day 7. The total dose of olanzapine will not exceed 10 mg daily during this study. Subjects will be monitored for adverse events and undergo blood sampling for glucose, insulin, and Hgb A1c on day 14. Vital signs, height, weight, and BMI will also be evaluated. Subjects will be instructed to bring their study medication with them on day 14 for assessment of study drug accountability.

Subjects will be contacted by phone at least once within 2 weeks following the day 14 visit to assess for potential side effects. Subjects may also come in for an extra/optional study visit between the Day 14 and Day 35 visits, if warranted by side effects.

Subjects will return on day 35 to monitor for adverse events, vital signs, height, weight, BMI, and glucose check.

During the study, subjects will rate their gastroparesis symptoms on a daily basis by completing the GCSI-DD and appetite VAS questionnaires. Subjects will also record daily the number of stools and their consistency [42]. Subjects will be asked to complete all diaries after the evening meal. The subjects will fast prior to returning to clinic on the morning of day 56 to undergo assessment of their gastric emptying time by WMC and complete an appetite VAS. Blood sampling for LFTs, glucose, insulin, Hgb A1c, and ghrelin levels will be performed. Vital signs, height, weight, and BMI will also be measured. All remaining study medication will be returned to the clinical unit for final drug accountability. Subjects will continue to rate their gastroparesis symptoms for 14 days following the end of dosing.

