8 DATA ANALYSIS

Procedure for Accounting for Missing, Unused, and Spurious Data: The primary outcome measure in our study is whether olanzapine is efficacious and safe for the treatment of idiopathic gastroparesis. We will use multiple imputation with 10 imputed datasets to replace missing values on outcome and predictor variables [46]. If 10 imputed datasets are not sufficient to ensure stability of estimates, we will use 20 imputed datasets. This allows for maximal use of available data while maximizing statistical power.

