10 STATISTICAL CONSIDERATIONS

Changes in measures from baseline will first be examined using descriptive statistics and graphical analysis. Significance of changes by the post treatment assessment will be determined using paired t tests or Wilcoxon rank sum tests, depending on the normality of the measures. Hierarchical regression will be used to analyze patterns of change across all measurement times, with time as a nested factor within subject. Adverse events will be summarized by proportions and 95% confidence intervals.

Sample size was based on variance estimates from prior studies using GCSI-DD and the appetite VAS in patients with gastroparesis [41, 47], and was computed using a 2-

sided type I error rate of 0.05. Conservatively using the largest variance reported for any of the GSCI subscales, and conservatively using a within-subject correlation of 0.6, a sample size of 10 patients will provide 88% power to detect a 1-point decrease in GCSI-DD, which we judged to be a clinically meaningful change in the subscales and total scale. For a more likely within-subject correlation of 0.8, power would be >99%. For the appetite VAS, we judged a 10 mm change to be clinically significant. Again conservatively using the largest of the reported variances, 10 patients will give 80% power to detect a 10mm change if the within-subject correlation is 0.6 and 97% power if the within-subject correlation is 0.8. A sample size of 10 subjects will also provide sufficient precision in parameter estimates from this study for use in power calculations for future studies of olanzapine in patients with gastroparesis.

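### Section 10 names an independent-samples test (Wilcoxon rank sum) as the non-normal fallback for a before-after comparison in one arm; the signed-rank test is needed

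*Combined protocol and SAP*

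**What the plan says.** Section 6 (Study Design and Procedures) describes 10 subjects and states: "This will be an open label trial without a placebo arm". Section 2 (Objectives) sets the comparison: the diary and the appetite scale are used to "compare severity of symptoms before and after treatment with olanzapine". No section describes two independent groups to be compared.

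Section 10 (Statistical Considerations) tests the significance of change with "paired t tests or Wilcoxon rank sum tests, depending on the normality of the measures", and adds a hierarchical regression across all measurement times. The next paragraph of that section sets the power, "conservatively using a within-subject correlation of 0.6" for the main case. For the appetite VAS it also gives "97% power if the within-subject correlation is 0.8". The signed-rank test does not appear in the documents.

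**The concern.** The two tests offered as alternatives do not answer the same design. The paired t test works on one difference per subject. The rank sum test pools all 20 values and treats the 10 baseline and 10 follow-up values as if they came from different people. It therefore discards the pairing on which the power statement rests.

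When the two values from a subject are positively correlated, the rank sum test is too strict: its real error rate falls below the nominal 5%, and true changes can be missed. How strict it is depends on the correlation. Section 10 gives correlations only for the GCSI-DD and the appetite VAS. It gives none for other before-after measures, such as gastric emptying time or the day-56 bloods in Section 6 ("Blood sampling for LFTs, glucose, insulin, Hgb A1c, and ghrelin levels will be performed"), so for those the real error rate of the fallback cannot be stated in advance.

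**Working it through.** **1. Does the stated power assume pairing?** No SD is given, so I solved for it from the stated power at r = 0.6, for a two-sided paired t test at 0.05 with n = 10:

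SD of difference = SD × √(2(1 − r)); noncentrality = Δ × √10 / SD of difference; power from the noncentral t on 9 df, critical value 2.262.

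| | Solved SD | Noncentrality, r = 0.6 | Noncentrality, r = 0.8 | Power at r = 0.8 | Stated at r = 0.8 |
|---|---|---|---|---|---|
| GCSI-DD, Δ = 1 point (88% at r = 0.6) | 1.00 | 3.53 | 4.99 | 99.3% | >99% |
| VAS, Δ = 10 mm (80% at r = 0.6) | 11.2 mm | 3.15 | 4.45 | 97.6% | 97% |

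The stated figures fit a paired analysis.

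**2. Why the rank sum test is too strict.** The mean before-after difference has variance 2·SD²(1 − r)/n, but the rank sum reference distribution corresponds to r = 0. The true spread is smaller by a factor of roughly √(1 − r): 0.63 at r = 0.6 and 0.45 at r = 0.8.

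**3. Type I error, by simulation.** Exact critical values for n = 10: rank sum U ≤ 23 (size 4.33% for independent samples) and signed-rank W ≤ 8 (size 4.88%). There were 60,000 trials per setting over five assumed shapes: normal, and lognormal with log-SD 0.5 and 1, each lognormal built in two ways.

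| r | Rank sum | Signed-rank |
|---|---|---|
| 0 | 4.2–4.3% | 4.7–5.1% at every r |
| 0.3 | 1.2–2.0% | |
| 0.4 | 0.7–1.4% | |
| 0.5 | 0.4–0.9% | |
| 0.6 | 0.2–0.7% | |
| 0.8 | 0.03–0.2% | |

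**4. Power if the fallback were always used, normal data** (100,000 trials per setting):

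| | Rank sum | Signed-rank |
|---|---|---|
| GCSI-DD, r = 0.6 | 53% | 86.6% |
| GCSI-DD, r = 0.8 | 56% | 98.9% |
| VAS, r = 0.6 | 41% | 78.1% |
| VAS, r = 0.8 | 42% | 97.0% |

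Under moderate skew (log-SD 0.5) and constant use, the loss at r = 0.6–0.8 is 15–36 points.

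**5. Power of the whole procedure.** The fallback runs only when normality is rejected. Section 10 gives no rule, so I assumed Shapiro-Wilk p < 0.05, with the paired t test otherwise (40,000 trials per setting).

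- Moderate skew, r = 0.6–0.8, check on the scores at either visit: fallback used in 28–41% of trials. Power with rank sum v signed-rank is 83–91% v 87–98% (GCSI-DD) and 75–86% v 81–95% (VAS), a loss of 4–10 points.
- Moderate skew, r = 0.6–0.8, check on the differences: fallback used in 12–15% of trials; loss 0–3 points.
- Normal data, r = 0.6–0.8: loss 1.5–4 points.
- Strong skew (log-SD 1), r = 0.6–0.8: from a gain of 7 points to a loss of 3 to 4.
- r = 0.3: normal data lose about 1 point at most, moderate skew gains 0–3, strong skew gains 7–13.

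Whole-procedure type I error, moderate skew, r = 0.6–0.8, rank sum v signed-rank: 3.1–3.5% v 4.5–4.7% (score check) and 4.0–4.1% v 4.8–4.9% (difference check).

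**The case against.** The strongest reply is that this is only a naming slip, which the section itself resolves. The sentence concerns changes, offers the rank test as the alternative to a paired test, and is followed by power figures built on within-subject correlation. An analyst would have to ignore all of that to run a rank sum test. The study is also a 10-patient open-label pilot, the regression keeps the pairing, and false positives are not inflated at correlations of 0 or above.

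Much of this stands. A slip is the likeliest explanation, and every loss above applies only if the text is followed literally. The sizes rest on assumptions: solved SDs (real ones may be smaller, since the plan says it used the largest reported variance), chosen lognormal shapes (log-SD 1 is doubtful for a bounded scale such as the VAS) and an assumed normality rule. The 10-point figure is not a bound, because heavier use of the fallback would cost more. The reference to normality of the measures could also mean normality of the changes, so that part is a request for clarity.

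None of this makes the named test right. A plan is carried out from its wording, software offers both tests under similar names, and the choice should not be left until the data are seen.

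**Conclusion.** The concern holds. A stated analysis rule names the wrong test, and this conclusion needs no simulation: one arm, the same subjects twice, and an independent-samples test. The practical consequence is modest and should be corrected before analysis. At the plan's own correlations of 0.6–0.8, literal use would test at about 0.7% or less rather than 5%. The overall power cost is at most about 10 points under moderate skew, given the assumed SDs, shapes and Shapiro-Wilk rule, and can reverse under strong skew or at a correlation of 0.3. Results from the paired t test and the hierarchical regression are not in question.

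**What to change.** In Section 10, replace the rank sum test with the Wilcoxon signed-rank test on the within-subject differences, and say that normality is judged on those differences.

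The cost is a few words; sample size, visits and data collection stay as they are. There are two trade-offs. The signed-rank test reads as a test of location only if the differences are roughly symmetric. Under strong skew its overall power can be up to 7 points below the rank sum's at r = 0.6–0.8, and up to 13 points below at r = 0.3. In return, its type I error stays near 5% whatever the correlation.

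Two additions are optional and not needed to cure the defect: a rule for ties and zero differences, and a rule for combining the rank test across imputed datasets, consistent with Section 8 ("We will use multiple imputation with 10 imputed datasets to replace missing values").

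### The longitudinal model nests time within subject: read literally it has no common time effect, and read loosely it leaves the false-positive rate for a trend uncontrolled

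*Combined protocol and SAP*

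**What the plan says.** Section 10 (Statistical Considerations) names two inferential analyses of change. The first is a comparison at one time point: "Significance of changes by the post treatment assessment will be determined using paired t tests or Wilcoxon rank sum tests". The second is the longitudinal model, described only by "Hierarchical regression will be used to analyze patterns of change across all measurement times, with time as a nested factor within subject".

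The section does not state a fixed time term, whether time is linear or categorical, the random effects, the residual covariance, a degrees-of-freedom method, or which measurement times enter.

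The data come from section 6. "This is a pilot study of 10 consecutive subjects", and all follow one calendar. Symptom diaries are kept before dosing "for a minimum of 7 days to determine baseline level of symptoms". On drug, "During the study, subjects will rate their gastroparesis symptoms on a daily basis by completing the GCSI-DD and appetite VAS questionnaires". Afterwards, "Subjects will continue to rate their gastroparesis symptoms for 14 days following the end of dosing". Weight, BMI, glucose, insulin and ghrelin are measured at visits only.

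A correlation between repeated measures appears only in the sample-size paragraph of section 10, "conservatively using a within-subject correlation of 0.6", with 0.8 given as the more likely value. No day-to-day correlation is given anywhere.

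**The concern.** A factor is nested when its levels belong to one subject only. Here day 14 is the same study day for everyone, so time is crossed with subject. Nesting it gives each subject a private set of time effects, and the model then has no parameter for the average course of symptoms, which is what the sentence sets out to describe.

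Multilevel analysts also use the word loosely, for occasions grouped within subjects. On that reading the sentence still supplies only a subject effect. Fitted as a random intercept, it treats the daily scores as independent once each subject's mean is removed. If neighbouring days resemble each other, or subjects change at different rates, the standard error of a time trend is then too small: hundreds of diary entries count as independent evidence although there are 10 independent units.

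This is the only planned analysis of the diary's time course. Section 6 uses the name post-treatment assessment for the visit 14 days after the last dose. If section 10 means that visit, the course of symptoms on drug rests on this model alone. Section 10 also expects estimates from this study to feed later power calculations, so standard errors that are too small would carry forward.

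**Working it through.** **Inputs.** From the protocol: 10 subjects; two-sided 5% level; at least 7 baseline, 56 on-drug and 14 post-dosing diary days. This gives 7 + 56 = 63 daily scores per subject, or 77 with the post-dosing days. Assumed: the serial correlation and the spread of slopes.

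**The plan's own figures.** The plan gives no error rate for this model, only power for a paired change. With SD of change = SD × √(2(1 − ρ)) and a paired t test on 9 df, 88% power for 1 point at ρ = 0.6 implies SD 1.00 and SD of change 0.90. The same SD at ρ = 0.8 gives 99.3%, against the stated >99%. For the appetite VAS, 80% for 10 mm implies SD 11.2 mm and gives 97.6%, against the stated 97%. The figures agree with each other. The 88% and 80% cannot be checked independently because the variance is not stated.

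**Literal reading.** A 63-level time factor nested in 10 subjects has 10 × 63 = 630 cells for 630 observations. Residual df = 630 − 630 = 0, and there is no common time term.

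**Loose reading, random intercept only.** In balanced data the estimated trend is the within-subject slope

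b = Σ(x − x̄)(y − ȳᵢ) / S, where S = 10 × Σ(x − x̄)² over study days,

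with SE = √(RSS / df / S) and df = 630 − 10 − 1 = 619. The comparator is each subject's own slope, tested by a one-sample t test on 9 df. Each setting was simulated 3,000 times with no true mean change, complete diaries and normal errors. The Monte Carlo standard error is √(0.05 × 0.95 / 3,000) = 0.4 points near 5% and √(0.25 / 3,000) = 0.9 points near 50%.

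False positives for a linear trend under AR(1) day-to-day correlation:

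| AR(1) | 63 daily scores | 77 daily scores | 6 visits (days 0, 7, 14, 35, 56, 70) | Per-subject slopes, 63 scores |
|---|---|---|---|---|
| 0 | 4.7% | 4.6% | 5.2% | 4.8% |
| 0.2 | 11.2% | 11.1% | 5.3% | 5.7% |
| 0.3 | 14.5% | 14.6% | 4.3% | 5.2% |
| 0.5 | 25.5% | 24.9% | 5.2% | 4.5% |
| 0.7 | 38.8% | 39.9% | 6.0% | 5.2% |
| 0.9 | 62.1% | 63.3% | 11.8% | 5.5% |

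False positives when subjects' slopes differ and there is no serial correlation:

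| SD of 56-day change, in residual SDs | 63 daily scores | 6 visits | Per-subject slopes, 63 scores |
|---|---|---|---|
| 0.25 | 9.8% | 5.7% | 5.0% |
| 0.5 | 20.7% | 7.4% | 4.2% |
| 1 | 45.0% | 14.8% | 4.4% |
| 1.5 | 57.3% | 20.4% | 4.7% |

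Repeat runs agreed within a few points: 10, 23, 46 and 59% for differing slopes on 63 days, and up to 13% for visits under AR(1). An on-drug versus baseline contrast on 63 days gave 21%, 32% and 46% at AR(1) 0.5, 0.7 and 0.9. A smaller check with fitted mixed models (150 trials per setting) gave 16, 21 and 36% at AR(1) 0.3, 0.5 and 0.7 with a random intercept, and 5 to 7% once a random slope was added.

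**Do the plan's correlations settle which row applies?** No. Under constant correlation, two 7-day means correlate at r = 7 × ICC / (1 + 6 × ICC). An ICC of 0.176 gives 1.232 / 2.056 = 0.60, and 0.364 gives 2.548 / 3.184 = 0.80. With those values the random-intercept test rejected 5.3% and 4.5% of the time, which is nominal.

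**The case against.** The strongest reply is that the sentence is ordinary multilevel shorthand. A competent analyst would add a fixed time effect and probably random slopes, and nothing in section 10 forbids either. That stands: the missing common time effect follows only from the literal reading, and the documents never mention a random intercept. But the plan does not require those terms, and the choice could be made after open-label data have been seen.

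Three stronger readings are tempting, and the documents do not support them.

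- A reader might infer that the false-positive rate simply is somewhere between 26% and 62%. That range is the case of AR(1) 0.5 to 0.9 on daily scores. No autocorrelation is given, and the rate is nominal when there is none.
- A reader might infer that the 0.6 to 0.8 correlations show subjects drifting between baseline and end of treatment. They do not, because constant correlation produces the same values with nominal error. There is some reason to expect differing trajectories: section 6 lets the dose change at days 7 and 14 on each subject's own response. That makes them plausible, not proven.
- A reader might infer that the trial's main test is compromised, or that no other analysis uses the diary. The paired comparison rests on one change per subject, so this inflation does not touch it, and for the GCSI-DD it must itself use diary scores. (Whether the rank test named there suits paired data is a separate question.)

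Section 10 also speaks of measures generally, and several are taken only at visits. If only visit times enter, the problem is much smaller.

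**Conclusion.** The concern holds as a specification fault that should be fixed. The one structural term the plan states does not fit the design: taken literally, it yields neither an average time course nor an error term.

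Taken loosely and fitted with a random intercept alone, it leaves the type I error of a trend anywhere from about 5% to over 60% on daily scores. With visit times only, the range is about 4 to 13% under AR(1) and up to about 20% with differing slopes. Where the rate falls depends on the assumed serial correlation and slope spread, and on the assumption that no further random terms are added. The calculations also assume complete diaries.

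Rating this as a fault that must be corrected before the trial can be interpreted would go too far. This is a 10-subject open-label pilot, the named paired comparison is unaffected, and the high error rates are conditional on assumptions.

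**What to change.** Replace the sentence in section 10 with a model that does the following:

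- names the measurement times that enter (for example, GCSI-DD and appetite VAS averaged by study week) and says whether post-dosing days are included;
- has time as a fixed effect crossed with subject;
- has a random intercept and a random slope for each subject, or a serial residual covariance such as AR(1);
- uses a small-sample degrees-of-freedom method such as Kenward-Roger;
- is labelled as supportive of the paired comparison.

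Weekly averaging alone is not enough, because a random intercept on its own can still understate the error of the trend. A simpler alternative is to compute each subject's slope or change and test the 10 values on 9 df, which gave 4 to 6% false positives in every setting. The choice among these is a matter of preference; the fixed time effect and an honest between-subject error term are not.

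The cost is one paragraph of text and no extra data. Confidence intervals will generally be wider than those from a random-intercept model.
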